8.11.2. Group 2 (0- and 36-Month Schedule)

8.11.2.1. Visit 1 (Day 1), Vaccination 1

In the case of temporary delay of vaccination, procedures and assessments below will be redone or reconfirmed, as applicable, on the day of vaccination.

- Obtain written informed consent, and assent if appropriate, before performing study-specific procedures. The date of informed consent will be recorded on the CRF.
- Record the participant's demographic information (including date of birth, sex, race, and ethnicity). The full date of birth will be collected to critically evaluate the immune response and safety profile by age.
- Record the presence of chronic conditions and/or medical history of significance, including relevant surgical procedures and cardiac medical history.
- Record previous PRP-OMP vaccinations as described in [Section 6.5](#).
- Perform a physical examination evaluating any clinically significant abnormalities within the following body systems: general appearance; skin; head, eyes, ears, nose, throat; heart; lungs; abdomen; extremities; neurological; musculoskeletal; and lymph nodes; including worsening of medical history conditions. Results must be recorded on source documents and the CRF. Findings from a physical examination conducted as part of standard routine care and before informed consent may be used for purposes of the study only if the examination was performed no more than 2 days before vaccination. A brief examination must be performed on the day of vaccination to document that no change in health has occurred in the interim.
- On the day of vaccination, perform a urine pregnancy test on female participants. A negative pregnancy test result is required before the participant may receive the study intervention.
- On the day of vaccination, prior to administration of study intervention, measure and record the participant's oral temperature.
- Ensure that all of the inclusion criteria, none of the exclusion criteria, and none of the temporary delay criteria are met.
- If a participant is eligible for the study, assign a randomization number and an investigational product container number via the IRT, or an equivalent system.
- On the day of vaccination, prior to administration of study intervention, collect a blood sample (approximately 25 mL). Collect the blood sample only if the participant is eligible for vaccination on the same day.

- The unblinded administrator administers a single 0.5-mL intramuscular injection of MenABCWY into the upper deltoid muscle of the arm. The time of study intervention administration will be recorded on the CRF.
- Observe the participant for at least 30 minutes (or longer as per local practice) after the study intervention administration for any acute reactions. Record any AEs observed during the 30-minute observation period; these AEs are defined as immediate AEs ([Section 8.2](#)).
- Record AEs as described in [Section 8.3](#) and the [SoA](#). Time of onset will be recorded for any AEs that occur on the same day as study intervention administration.
- Record concomitant medications used to treat AEs as described in [Section 6.5](#).
- Provide the parent(s)/legal guardian with a contact card ([Section 10.1.10](#)).
- Ask the parent(s)/legal guardian to contact the investigator immediately if any significant illness or hospitalization occurs.
- Schedule an appointment for the next study visit, and confirm that it is scheduled within the time window per protocol.
- Complete the source documents.
- Complete the CRF, and update the study intervention accountability records.

8.11.2.2. Visit 2, Month 1 (1 Month [28 to 42 Days] After Visit 1), 1-Month Post-Vaccination 1 Blood Draw

- Ensure that the participant continues to be eligible for the study and continues to comply with contraception requirements detailed in [Section 5](#).
- Ensure that the participant continues to meet none of the withdrawal criteria as described in [Section 7](#) and none of the temporary delay of blood draw criteria as described in [Section 5.5.2](#).
- Complete the Study Visit/Telephone Contact AE Checklist to:
 - Inquire whether the participant had any NDCMCs since the last visit. Inquire whether the participant had any of the following related to an AE since the last visit: hospitalizations, visits to other medical facilities, medication use, or missed days of school or work. Please refer to the ISF for additional details.
 - Inquire about neuroinflammatory and autoimmune conditions, such as transverse myelitis, uveitis, optic neuritis, and multiple sclerosis. Please refer to the ISF for additional details.

- Record AEs as described in [Section 8.3](#) and the [SoA](#).
- Review AEs that were ongoing since the previous visit, and record their end dates or confirm that they are still continuing.
- Record concomitant medications used to treat AEs as described in [Section 6.5](#).
- Record nonstudy vaccinations as described in [Section 6.5](#).
- Collect a blood sample (approximately 25 mL).
- Provide the parent(s)/legal guardian with a memory aid. Instruct the parent(s)/legal guardian to use the memory aid between Visits 2 and 3 to remind him or her to review any significant illnesses, hospitalizations, NDCMCs, or visits to a medical facility with study site personnel. The memory aid is not a diary for the collection of reactogenicity. Please refer to the ISF for additional details.
- Ask the parent(s)/legal guardian to contact the investigator immediately if any significant illness or hospitalization occurs.
- Schedule a telephone contact, and confirm that it is scheduled within the time window per protocol.
- Complete the source documents.
- Complete the CRFs.

8.11.2.3. Visit 3, Month 6 (6 Months [168 to 196 Days] After Visit 1), Safety Telephone Contact 1

- Contact the parent(s)/legal guardian by telephone.
- Ensure that the participant continues to be eligible for the study and continues to comply with contraception requirements detailed in [Section 5](#).
- Ensure that the participant continues to meet none of the withdrawal criteria as described in [Section 7](#).
- Complete the Study Visit/Telephone Contact AE Checklist to:
 - Inquire whether the participant had any NDCMCs since the last visit. Inquire whether the participant had any of the following related to an AE since the last visit: hospitalizations, visits to other medical facilities, medication use, or missed days of school or work. Please refer to the ISF for additional details.

- Inquire about neuroinflammatory and autoimmune conditions, such as transverse myelitis, uveitis, optic neuritis, and multiple sclerosis. Please refer to the ISF for additional details.
- Record AEs as described in [Section 8.3](#) and the [SoA](#).
- Review AEs that were ongoing since the previous visit, and record their end dates or confirm that they are still continuing.
- Record concomitant medications used to treat AEs as described in [Section 6.5](#).
- Record nonstudy vaccinations as described in [Section 6.5](#).
- Schedule an appointment for the next study visit, and confirm that it is scheduled within the time window per protocol.
- Complete the source documents.
- Complete the CRFs.

8.11.2.4. Visit 4, Month 12 (12 Months [336 to 394 Days] After Visit 1), Vaccination 2

In the case of temporary delay of vaccination, procedures and assessments below will be redone or reconfirmed, as applicable, on the day of vaccination.

- Ensure that the participant continues to be eligible for the study and continues to comply with contraception requirements detailed in [Section 5](#).
- Ensure that the participant continues to meet none of the withdrawal criteria as described in [Section 7](#) and none of the temporary delay of vaccination criteria as described in [Section 5.5.1](#).
- Perform a brief physical examination of the participant's general appearance, skin, ears, throat, heart, lungs, abdomen, and lymph nodes.
- Complete the Study Visit/Telephone Contact AE Checklist to:
 - Inquire whether the participant had any NDCMCs since the last visit. Inquire whether the participant had any of the following related to an AE since the last visit: hospitalizations, visits to other medical facilities, medication use, or missed days of school or work. Please refer to the ISF for additional details.
 - Inquire about neuroinflammatory and autoimmune conditions, such as transverse myelitis, uveitis, optic neuritis, and multiple sclerosis. Please refer to the ISF for additional details.

- Record AEs as described in [Section 8.3](#) and the [SoA](#). Time of onset will be recorded for any AEs that occur on the same day as study intervention administration.
- Review AEs that were ongoing since the previous visit, and record their end dates or confirm that they are still continuing.
- Record concomitant medications used to treat AEs as described in [Section 6.5](#).
- Record nonstudy vaccinations as described in [Section 6.5](#).
- On the day of vaccination, perform a urine pregnancy test on female participants. A negative pregnancy test result is required before the participant may receive the study intervention.
- On the day of vaccination, prior to administration of study intervention, measure and record the participant's oral temperature.
- The unblinded administrator administers a single 0.5-mL intramuscular injection of saline placebo into the upper deltoid muscle of the arm. The time of study intervention administration will be recorded on the CRF.
- Observe the participant for at least 30 minutes (or longer as per local practice) after the study intervention administration for any acute reactions. Record any AEs observed during the 30-minute observation period; these AEs are defined as immediate AEs ([Section 8.2](#)).
- Ask the parent(s)/legal guardian to contact the investigator immediately if any significant illness or hospitalization occurs.
- Schedule an appointment for the next study visit, and confirm that it is scheduled within the time window per protocol.
- Complete the source documents.
- Complete the CRFs.

8.11.2.5. Visit 5, Month 13 (1 Month [28 to 42 Days] After Visit 4), 1-Month Post-Vaccination 2 Blood Draw

- Ensure that the participant continues to be eligible for the study and continues to comply with contraception requirements detailed in [Section 5](#).
- Ensure that the participant continues to meet none of the withdrawal criteria as described in [Section 7](#) and none of the temporary delay of blood draw criteria as described in [Section 5.5.2](#).

- Complete the Study Visit/Telephone Contact AE Checklist to:
 - Inquire whether the participant had any NDCMCs since the last visit. Inquire whether the participant had any of the following related to an AE since the last visit: hospitalizations, visits to other medical facilities, medication use, or missed days of school or work. Please refer to the ISF for additional details.
 - Inquire about neuroinflammatory and autoimmune conditions, such as transverse myelitis, uveitis, optic neuritis, and multiple sclerosis. Please refer to the ISF for additional details.
- Record AEs as described in [Section 8.3](#) and the [SoA](#).
- Review AEs that were ongoing since the previous visit, and record their end dates or confirm that they are still continuing.
- Record concomitant medications used to treat AEs as described in [Section 6.5](#).
- Record nonstudy vaccinations as described in [Section 6.5](#).
- Collect a blood sample (approximately 25 mL).
- Provide the parent(s)/legal guardian with a memory aid. Instruct the parent(s)/legal guardian to use the memory aid between Visits 5 and 10 to remind him or her to review any significant illnesses, hospitalizations, NDCMCs, or visits to a medical facility with study site personnel. The memory aid is not a diary for the collection of reactogenicity. Please refer to the ISF for additional details.
- Ask the parent(s)/legal guardian to contact the investigator immediately if any significant illness or hospitalization occurs.
- Schedule an appointment for the next study visit as an in-person visit to maintain blinding, and confirm that it is scheduled within the time window per the protocol. Convert the scheduled next study visit to a telephone contact after the study-planned unblinding occurs.
- Complete the source documents.
- Complete the CRFs.

8.11.2.6. Visit 8, Month 24 (12 Months [336 to 394 Days] After Visit 4), Safety Telephone Contact 2

Visit 8 must not be performed until the investigator is unblinded. The Visit 8 window may be extended for individual participants by up to 60 days, at the discretion of the sponsor, to ensure unblinded information is available.

- Contact the parent(s)/legal guardian by telephone.
- Ensure that the participant continues to be eligible for the study and continues to comply with contraception requirements detailed in [Section 5](#).
- Ensure that the participant continues to meet none of the withdrawal criteria as described in [Section 7](#).
- Complete the Study Visit/Telephone Contact AE Checklist to:
 - Inquire whether the participant had any NDCMCs since the last visit. Inquire whether the participant had any of the following related to an AE since the last visit: hospitalizations, visits to other medical facilities, medication use, or missed days of school or work. Please refer to the ISF for additional details.
 - Inquire about neuroinflammatory and autoimmune conditions, such as transverse myelitis, uveitis, optic neuritis, and multiple sclerosis. Please refer to the ISF for additional details.
- Record AEs as described in [Section 8.3](#) and the [SoA](#).
- Review AEs that were ongoing since the previous visit, and record their end dates or confirm that they are still continuing.
- Record concomitant medications used to treat AEs as described in [Section 6.5](#).
- Record nonstudy vaccinations as described in [Section 6.5](#).
- Schedule an appointment for the next study visit, and confirm that it is scheduled within the time window per protocol.
- Complete the source documents.
- Complete the CRFs.

8.11.2.7. Visit 9, Month 36 (24 Months [700 to 756 Days] After Visit 4), Vaccination 3

In the case of temporary delay of vaccination, procedures and assessments below will be redone or reconfirmed, as applicable, on the day of vaccination.

- Ensure that the participant continues to be eligible for the study and continues to comply with contraception requirements detailed in [Section 5](#).
- Ensure that the participant continues to meet none of the withdrawal criteria as described in [Section 7](#) and none of the temporary delay of vaccination criteria as described in [Section 5.5.1](#).

- Perform a brief physical examination of the participant’s general appearance, skin, ears, throat, heart, lungs, abdomen, and lymph nodes. Record any AEs as described in [Section 8.3](#).
- Complete the Study Visit/Telephone Contact AE Checklist to:
 - Inquire whether the participant had any NDCMCs since the last visit. Inquire whether the participant had any of the following related to an AE since the last visit: hospitalizations, visits to other medical facilities, medication use, or missed days of school or work. Please refer to the ISF for additional details.
 - Inquire about neuroinflammatory and autoimmune conditions, such as transverse myelitis, uveitis, optic neuritis, and multiple sclerosis. Please refer to the ISF for additional details.
- Record AEs as described in [Section 8.3](#) and the [SoA](#). Time of onset will be recorded for any AEs that occur on the same day as study intervention administration.
- Review AEs that were ongoing since the previous visit, and record their end dates or confirm that they are still continuing.
- Record concomitant medications used to treat AEs as described in [Section 6.5](#).
- Record nonstudy vaccinations as described in [Section 6.5](#).
- On the day of vaccination, perform a urine pregnancy test on female participants. A negative pregnancy test result is required before the participant may receive the study intervention.
- On the day of vaccination, prior to administration of study intervention, measure and record the participant’s oral temperature.
- Administer a single 0.5-mL intramuscular injection of MenABCWY into the upper deltoid muscle of the arm. The time of study intervention administration will be recorded on the CRF.
- Observe the participant for at least 30 minutes (or longer as per local practice) after the study intervention administration for any acute reactions. Record any AEs observed during the 30-minute observation period; these AEs are defined as immediate AEs ([Section 8.2](#)).
- Ask the parent(s)/legal guardian to contact the investigator immediately if any significant illness or hospitalization occurs.
- Schedule an appointment for the next study visit, and confirm that it is scheduled within the time window per protocol.

- Complete the source documents.
- Complete the CRFs.

8.11.2.8. Visit 10, Month 37 (1 Month [28 to 42 Days] After Visit 9), 1-Month Post-Vaccination 3 Blood Draw

- Ensure that the participant continues to be eligible for the study and continues to comply with contraception requirements detailed in [Section 5](#).
- Ensure that the participant continues to meet none of the withdrawal criteria as described in [Section 7](#) and none of the temporary delay of blood draw criteria as described in [Section 5.5.2](#).
- Complete the Study Visit/Telephone Contact AE Checklist to:
 - Inquire whether the participant had any NDCMCs since the last visit. Inquire whether the participant had any of the following related to an AE since the last visit: hospitalizations, visits to other medical facilities, medication use, or missed days of school or work. Please refer to the ISF for additional details.
 - Inquire about neuroinflammatory and autoimmune conditions, such as transverse myelitis, uveitis, optic neuritis, and multiple sclerosis. Please refer to the ISF for additional details.
- Record AEs as described in [Section 8.3](#) and the [SoA](#).
- Review AEs that were ongoing since the previous visit, and record their end dates or confirm that they are still continuing.
- Record concomitant medications used to treat AEs as described in [Section 6.5](#).
- Record nonstudy vaccinations as described in [Section 6.5](#).
- Collect a blood sample (approximately 25 mL).
- Ask the parent(s)/legal guardian to contact the investigator immediately if any significant illness or hospitalization occurs.
- Complete the source documents.
- Complete the CRFs.

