1.2. Schema

Group 1 (0- and 12-Month Schedule)							
	Vaccination 1	1 Month Post–Vaccination 1 Blood Draw	Safety Telephone Contact 1	Vaccination 2	1 Month Post–Vaccination 2 Blood Draw	12-Month Antibody Persistence Visit	24-Month Antibody Persistence Visit
Approximate Month	0	1	6	12	13	24	36
Visit Number	1	2	3	4	5	6	7 ^a
Group 1 (n=150)	MenABCWY			MenABCWY			
Blood draw	25 mL	25 mL			25 mL	25 mL	25 mL

a. Visits 8, 9, and 10 will not be conducted for Group 1 participants.

Group 2 (0- and 36-Month Schedule)								
	Vaccination 1	1 Month Post–Vaccination 1 Blood Draw	Safety Telephone Contact 1	Vaccination 2	1 Month Post–Vaccination 2 Blood Draw	Safety Telephone Contact 2	Vaccination 3	1 Month Post–Vaccination 3 Blood Draw
Approximate Month	0	1	6	12	13	24	36	37
Visit Number	1	2	3	4	5 ^a	8 ^b	9	10
Group 2 (n=150)	MenABCWY			Saline			MenABCWY	
Blood draw	25 mL	25 mL			25 mL			25 mL

a. Visits 6 and 7 will not be conducted for Group 2 participants.

b. Visit 8 will be scheduled as an in-person visit to maintain the blind and converted to a telephone visit once unblinding has occurred.

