6.3.2. Blinding of Site Personnel

In this observer-blinded study, the study staff dispensing, preparing, and administering the vaccine will be unblinded. All other study and site personnel, including the investigator, investigator staff, participants, and participants' parent(s)/legal guardian, will be blinded to study intervention assignments through and including Visit 5 (Vaccinations 1 and 2). In particular, the individuals who evaluate participant safety will be blinded. Because the study vaccine and placebo are different in physical appearance, the study vaccine syringes will be administered in a manner that prevents the study participants from identifying the vaccine type based on its appearance. The second dose of MenABCWY for participants in Group 2 (Vaccination 3) will be given in an open-label manner.

The responsibility of the unblinded dispenser and administrator must be assigned to an individual or individuals who will not participate in the evaluation of any study participants. Contact between the unblinded dispenser and study participants and unblinded administrator and study participants should be kept to a minimum. The remaining site personnel must not know study intervention assignments.

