6.3.5. Planned Unblinding

Pfizer will release unblinding information to the investigators after all participants have completed the blood draw at Visit 5 (1 month after the second dose of MenABCWY in Group 1 [0- and 12-month schedule] or 1 month after placebo in Group 2 [0- and 36-month schedule]). Additional information is included in the ISF.

The second dose of MenABCWY in Group 2 (0- and 36-month schedule) will be administered in an open-label manner.

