- Observe the participant for at least 30 minutes (or longer as per local practice) after the study intervention administration for any acute reactions. Record any AEs observed during the 30-minute observation period; these AEs are defined as immediate AEs ([Section 8.2](#)).
- Ask the parent(s)/legal guardian to contact the investigator immediately if any significant illness or hospitalization occurs.
- Schedule an appointment for the next study visit, and confirm that it is scheduled within the time window per protocol.
- Complete the source documents.
- Complete the CRFs.

8.11.1.5. Visit 5, Month 13 (1 Month [28 to 42 Days] After Visit 4), 1-Month Post-Vaccination 2 Blood Draw

- Ensure that the participant continues to be eligible for the study and continues to comply with contraception requirements detailed in [Section 5](#).
- Ensure that the participant continues to meet none of the withdrawal criteria as described in [Section 7](#) and none of the temporary delay of blood draw criteria as described in [Section 5.5.2](#).
- Complete the Study Visit/Telephone Contact AE Checklist to:
 - Inquire whether the participant had any NDCMCs since the last visit. Inquire whether the participant had any of the following related to an AE since the last visit: hospitalizations, visits to other medical facilities, medication use, or missed days of school or work. Please refer to the ISF for additional details.
 - Inquire about neuroinflammatory and autoimmune conditions, such as transverse myelitis, uveitis, optic neuritis, and multiple sclerosis. Please refer to the ISF for additional details.
- Record AEs as described in [Section 8.3](#) and the [SoA](#).
- Review AEs that were ongoing since the previous visit, and record their end dates or confirm that they are still continuing.
- Record concomitant medications used to treat AEs as described in [Section 6.5](#).
- Record nonstudy vaccinations as described in [Section 6.5](#).
- Collect a blood sample (approximately 25 mL).
- Provide the parent(s)/legal guardian with a memory aid. Instruct the parent(s)/legal guardian to use the memory aid between Visits 5 and 6 to remind him or her to review any significant illnesses, hospitalizations, NDCMCs, or visits to a medical facility with study site personnel. The memory aid is not a diary for the collection of reactogenicity. Please refer to the ISF for additional details.

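### The Visit 5 memory-aid instruction names a visit that exists in only one group, so staff who must be blinded cannot follow it as written

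*Protocol*

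**What the plan says.** **Blinding rule.** Protocol Section 6.3.2 makes one exception to site blinding: "the study staff dispensing, preparing, and administering the vaccine will be unblinded". All other site personnel, together with participants and their parents or guardians, "will be blinded to study intervention assignments through and including Visit 5 (Vaccinations 1 and 2"). Section 6.2.1 repeats this for participants. Section 6.3.5 sets the release of codes by the last participant, not by each participant: "Pfizer will release unblinding information to the investigators after all participants have completed the blood draw at Visit 5".

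**Visit 5 procedures.** These are written separately by group. Section 8.11.1.5 (Group 1) reads "Instruct the parent(s)/legal guardian to use the memory aid between Visits 5 and 6". Section 8.11.2.5 (Group 2) reads "Instruct the parent(s)/legal guardian to use the memory aid between Visits 5 and 10". The booking bullets also differ. Group 1 has a generic line about scheduling the next visit. Group 2 has "Schedule an appointment for the next study visit as an in-person visit to maintain blinding", followed by conversion to a telephone contact after planned unblinding.

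**Visit map.** The Section 1.2 schema footnotes state "Visits 8, 9, and 10 will not be conducted for Group 1 participants" and "Visits 6 and 7 will not be conducted for Group 2 participants".

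**The concern.** At Visit 5 the blinded contrast is MenABCWY against saline at Month 12. The memory-aid step asks a blinded staff member to name a visit number to the parent, and the correct number depends on the group. Whoever performs the step must either know the assignment already or depart from the text.

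The stake is the safety description, which is a primary objective. AEs from the Vaccination 2 phase that are still open at Visit 5 are followed until they resolve or stabilise (Section 8.3.3). The investigator may also revise a causality opinion as information arrives (Appendix 3). Parents are asked to call at once about any significant illness. If the assignment is known during this time, those judgements and calls can differ by group.

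**Working it through.** No sample-size, power or error-rate figure bears on this point, so there is none to reproduce. The check sets the passages side by side and then applies arithmetic to the visit windows.

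**1. Does the visit number identify the group?**

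| Number named at Visit 5 | Group in which it exists (Section 1.2) | Month 12 injection |
|---|---|---|
| Visit 6 | Group 1 only | MenABCWY |
| Visit 10 | Group 2 only | Saline |

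The mapping is one to one. Under 1:1 allocation, the chance of naming the group correctly goes from 0.5 to 1.0 for anyone who knows the map.

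**2. Can an unblinded person take over the step?** The Visit 4 injection is assigned to the unblinded administrator (Sections 8.11.1.4 and 8.11.2.4). No Visit 5 step is assigned to unblinded staff. Section 6.3.2 also bars unblinded dispensers and administrators from evaluating participants and asks that their contact with participants be minimal. As written, the step falls to blinded staff.

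**3. Do the other Visit 5 steps differ by group?** The AE checklist, AE recording, concomitant medication, nonstudy vaccination and blood-draw bullets have the same wording in both sections, and all come before the memory-aid bullet. The booking bullets differ in wording but lead to the same action. Visit 6 is a blood-draw visit and therefore in person, Visit 8 is booked in person, and both have a window of 336 to 394 days after Visit 4.

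**4. How long could early disclosure last?** It runs from a participant's own Visit 5 to code release. Visits 6 and 8 must not take place before the investigator is unblinded, so the time to that visit is the ceiling. Visit 5 falls 28 to 42 days after Visit 4.

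- Shortest time from Visit 5 to the next visit: 336 − 42 = 294 days.
- Longest: 394 − 28 = 366 days.
- Longest with the 60-day extension allowed for Visits 6 and 8: (394 + 60) − 28 = 426 days.

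These are bounds from the windows. The actual length for a given participant is the time from that participant's Visit 5 to code release, which follows the last participant's Visit 5. That depends on accrual, and neither document gives accrual.

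**5. How much of the analysed safety period falls in that time?** In SAP Table 5, follow-up phase 2 starts the day after Visit 5 and ends 6 months after Vaccination 2. The table's note takes 6 months as 183 days for Interval 11. If the same is assumed here, the phase lasts 183 − 42 = 141 to 183 − 28 = 155 days. Only events reported spontaneously before code release are exposed. Scheduled collection of these events is at Visit 6 or Visit 8, after unblinding by plan.

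**6. Does the memory-aid range agree with the rest of the protocol?** Section 8.2 has the aid in use at Visits 3, 6, 7, 8 and 10. The Group 1 range stops at Visit 6 although Section 8.2 includes Visit 7. The Group 2 range runs past Visit 8, where Section 8.2 already has it used. The ranges need reconciling whatever is decided on blinding.

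**The case against.** The strongest reply is that this is one visit number in a bullet. A family can decode it only if it knows the visit map. Both memory-aid bullets defer to the investigator site file for details, and that file, which is not among the documents, may already use common wording. Section 8.11 is laid out by group throughout, and nothing shows that it is the text handed to blinded staff. All of this limits the likely size. It does not remove the conflict inside the protocol, which staff do hold.

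A reader might also infer several stronger consequences. The documents do not support them:

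- *The booking step breaks the blind too.* Both groups are booked in person in the same window, and conversion to telephone comes only after unblinding. The wording could be aligned, but the action does not disclose the group.
- *Staff know the product while eliciting Visit 5 AEs.* The elicitation steps are identical in wording and come first, so no group-specific instruction is needed to carry them out.
- *The 6-month SAE, MAE and NDCMC percentages are compromised.* Their scheduled collection is unblinded by design, so only earlier spontaneous reports could be affected.
- *Group 2 families will leave or seek vaccine elsewhere, shrinking the evaluable set.* Planned unblinding precedes Visit 8 at about Month 24, and the second MenABCWY dose is at Month 36, so these families will know about the saline for about a year in any case. No figure in the documents links earlier knowledge to loss.

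**Conclusion.** The conflict is real and should be corrected. The protocol requires blinding through and including Visit 5, and the memory-aid step at that visit cannot be carried out as written by blinded staff. If followed literally, it applies to everyone who attends Visit 5, up to the planned 300 or so participants.

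The likely effect is confined to AE and causality judgements, and spontaneous safety reports, between a participant's own Visit 5 and code release. Serology is not exposed, because Section 6.3.3 keeps laboratory staff blinded to vaccine and visit number throughout. Immunogenicity is described within each group with no hypothesis test. The figures of 366 and 426 days should not be read as the expected duration of early disclosure; they are ceilings.

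The conclusion assumes that Section 8.11 is followed as written and that the investigator site file does not override it.

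**What to change.** Use identical memory-aid text in Sections 8.11.1.5 and 8.11.2.5, naming no group-specific visit. For example: *use the memory aid from now until the next study contact (about Month 24)*.

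For consistency, put the same in-person booking wording in both sections. State the conversion to telephone for Group 2 only as a step after planned unblinding.

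Give any group-specific memory-aid instruction for later visits after planned unblinding, at Visit 6 or Visit 8, and reconcile it with Section 8.2. No further hand-out of the aid is needed: the schedule of activities provides it only at Visits 2 and 5, and that can stay.

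The cost is the rewording of these bullets and, if it names visits, of the memory-aid form. Any matching text in the investigator site file should be checked at the same time.
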